## 9.6 Secondary Endpoints

The secondary efficacy endpoints consist of the following:

- Proportion of mild/moderate bleeding episodes successfully treated according to the same criteria as the primary endpoint of efficacy, at all other timepoints

- Proportion of bleeding episodes (mild/moderate and severe, separately and combined) with a “good” or “excellent” patient (and/or physician when available) reported assessment of efficacy at all timepoints
- Time to assessment of a “good” or “excellent” response of the bleeding episodes (mild/moderate and severe, separately and combined) by the patient (and/or physician when available)
- Descriptive analysis of the number of administrations and mean total amount of drug administered per bleeding episode

For each treatment regimen and both treatment regimens together, the proportions of bleeding episodes successfully treated, according to the same criteria as the primary endpoint of efficacy at all timepoints will be summarized using descriptive statistics, and a 95% CI for the true mean patient level proportion will be calculated based on normal approximation.

For each treatment regimen and both treatment regimens together, the proportions of bleeding episodes with a “good” or “excellent” patient reported assessment of the efficacy at all timepoints will be summarized using descriptive statistics, and a 95% CI for the true proportion will be calculated based on normal approximation.

The time to assessment of a “good” or “excellent” response of the bleeding episodes (mild/moderate and severe, separately and combined) by the patient/parent will be analyzed at the bleeding episode level using the K-M method to estimate the survival distribution for this endpoint for each treatment regimen separately and combined. Patients who receive rescue treatment at any time will be considered failures and will be assigned a censored value at the final timepoint. Patients who do not achieve a “good” or “excellent” response will be censored at the time of last response.

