## 9 PLANNED STATISTICAL METHODS

### 9.1 General Considerations

This section outlines the key components of the planned statistical analyses. Detailed methodology for the statistical analyses will be documented in a Statistical Analysis Plan (SAP). The SAP may modify the plan outlined in the protocol; however, any major modifications will also be reflected in a protocol amendment. If after database lock changes are made to the SAP, these deviations will be documented in the Clinical Study Report (CSR).

All data collected in this study will be documented using summary tables and patient data listings. Continuous variables will be summarized using descriptive statistics, specifically the sample size (n), mean, median, standard deviation, minimum and maximum. Categorical variables will be summarized by frequencies and percentages.

Where applicable, analyses will be done for all patients and by age group (aged from birth to  $<6$  years and  $\geq 6$  years to  $<12$  years).

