### 9.2 Determination of Sample Size

The proportion ( $\hat{p}$ ) of mild/moderate bleeding episodes treated with each dose of LR769 that are classified as being successfully treated will be compared with an objective performance criterion (OPC) of 0.55. A one-sided, one-sample normal approximation test, with an alpha = 0.0125 (adjusted from 0.025 to 0.0125 to account for multiplicity of testing), will be used to test the null hypothesis that  $p \leq 0.55$  versus the alternative hypothesis that  $p > 0.55$ , where  $p$  is the true proportion of mild/moderate bleeding episodes that are classified as successes. (Note: The standard error used in the denominator of the test statistic will account for the correlation among bleeding episodes for a given patient.) This will be done for each treatment regimen.

With the assumptions of a true proportion of success of 0.70, a correlation among bleeding episodes for a given patient of 0.1, and an OPC of 0.55, a sample size of 22 patients with a total of 352 mild/moderate bleeding episodes (assuming 8 bleeding episodes per treatment regimen per patient) will provide statistical power  $\geq 80\%$ . The study will enroll at least 24 patients, in order to account for dropouts and potential unevaluable bleeding episodes.

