## 9.5 Primary Endpoint

### 9.5.1 Primary Efficacy Endpoint

The primary efficacy endpoint for this study is defined as successful treatment of a bleeding episode at 12 hours after first administration of the study drug. The following are clarification definitions to satisfy regulatory requirements in multiple regions (i.e., the FDA and the EMA).

For primary efficacy endpoint for the FDA, only mild/moderate bleeding episodes are taken into account. Severe bleeding episodes will be a minority of the bleeding episodes treated in the study, and require further treatment even if the bleeding has improved. Efficacy in severe bleeding episodes will be analyzed separately, using descriptive statistics only.

The primary efficacy endpoint for the FDA is defined as the successful treatment of a bleeding episode at 12 hours (bleeding episode level), where a success is defined as meeting all of the following criteria:

- *Good or Excellent* response noted by patient/parent/guardian, depending on patient's age and maturity
- Study drug treatment: No further treatment with study drug beyond timepoint where a Good or Excellent response for this bleeding episode was noted
- No other hemostatic treatment needed for this bleeding episode
- No administration of blood products indicating continuation of bleeding beyond timepoint where a Good or Excellent response for this bleeding episode was noted
- No increase of pain beyond timepoint where a Good or Excellent response for this bleeding episode was noted that cannot be explained other than as continuation of bleeding

For each LR769 treatment, the proportion ( $\hat{p}$ ) of mild/moderate bleeding episodes rated as successfully treated at 12 hours will be summarized using the count and percentage. A 95%

normal approximation CI for the true percentage will be calculated taking into account the correlation between bleeding episodes for a given patient in calculating the standard error of the estimate  $\hat{p}$ .

The null and alternative hypotheses for the primary efficacy endpoint are as follows:

$$H_0: p \leq 0.55$$

$$H_1: p > 0.55.$$

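### Protocol Sections 9.5.1 and 9.6 leave unclear whether severe bleeds get a confidence interval; if they do, the normal approximation is the wrong one for small cells

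*Protocol*

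**What the plan says.** Protocol Section 9.6 lists among the secondary endpoints the "Proportion of bleeding episodes (mild/moderate and severe, separately and combined) with a" good/excellent rating, at all timepoints. A later paragraph of that section summarizes the good/excellent proportions "For each treatment regimen and both treatment regimens together", "and a 95% CI for the true proportion will be calculated based on normal approximation". It makes no exception for severe bleeds or for sparse cells, and it does not mention within-patient correlation.

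Section 9.5.1 takes a different line: "Severe bleeding episodes will be a minority of the bleeding episodes treated in the study", and "Efficacy in severe bleeding episodes will be analyzed separately, using descriptive statistics only". No expected number of severe bleeds is given anywhere.

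Section 9.1 adds a possible further split: "Where applicable, analyses will be done for all patients and by age group".

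The SAP supplied is an addendum to a main SAP that was not supplied. The addendum names no interval method for proportions. Its stratified tables for this endpoint (Section 2) cover mild/moderate bleeds alone and all severities combined. Severe bleeds on their own appear only in its time plots.

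**The concern.** Read together, the endpoint list and the interval sentence of Section 9.6 give severe bleeds their own normal-approximation interval, whereas Section 9.5.1 may mean that they get none. A programmer could follow either.

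If Section 9.6 is followed, the method is fragile where data are few. The standard error of a proportion is zero at 0% and at 100%, so an all-success cell prints as 100% to 100% however few bleeds it holds. Near those ends the limits can also pass 0% or 100%. Adjusting for correlation does not help, because a cluster-adjusted or patient-level standard error is also zero when every bleed succeeds.

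Protocol Table 1 describes severe bleeds as potentially threatening life or limb. An interval labelled 95% that shows no uncertainty for them would mislead a reader about how much the trial has learned.

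**Working it through.** **The plan's own figure.** The plan states no figure for this interval. The nearest is the power of at least 80% in Section 9.2, under "a true proportion of success of 0.70, a correlation among bleeding episodes for a given patient of 0.1, and an OPC of 0.55", with 22 patients and 8 bleeds per regimen each (176 per regimen).
- Design effect: 1 + (8 - 1) × 0.1 = 1.7. Effective n: 176/1.7 = 103.5.
- Standard error under the null: √(0.55 × 0.45/103.5) = 0.0489. Under the alternative: √(0.70 × 0.30/103.5) = 0.0450. Critical value at one-sided 0.0125: 2.241.
- Power with the null standard error: Φ((0.15 - 2.241 × 0.0489)/0.0450) = 0.815. With the alternative standard error: Φ(0.15/0.0450 - 2.241) = 0.862.

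The figure is reproduced. It concerns mild/moderate bleeds, so the primary test is not in question here.

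**Inputs for the severe-bleed check.** All are assumptions, because the documents give no count.
- 4 to 20 severe bleeds per regimen. Beside 176 mild/moderate bleeds, this is 4/180 = 2% to 20/196 = 10% of treated bleeds.
- True good/excellent rates of 70%, 80% and 90%. The 70% is the protocol's planning rate, set for the stricter mild/moderate primary endpoint.
- Independent bleeds.

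**Method.** The normal-approximation interval is p̂ ± 1.96 √(p̂(1 - p̂)/n). Coverage is the sum of the binomial probabilities of those results x whose interval contains the true rate.

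**One case by hand: n=4, true rate 90%.**
- x=4 gives 100% to 100%, which misses; probability 0.9⁴ = 0.656.
- x=3 gives 0.75 ± 0.424, or 0.326 to 1.174, which covers; probability 4 × 0.9³ × 0.1 = 0.292.
- x=2 gives 0.50 ± 0.49, or 0.01 to 0.99, which covers; probability 6 × 0.9² × 0.1² = 0.049.
- x=1 and x=0 miss.

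Coverage is 0.292 + 0.049 = 0.340, and the chance of a zero-width interval is 0.656.

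**All cases** (each cell shows true rates 70% / 80% / 90%):

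| n | Normal-approximation coverage | Chance of zero width | Wilson coverage | Clopper-Pearson coverage |
|---|---|---|---|---|
| 4 | 0.676 / 0.563 / 0.340 | 0.248 / 0.411 / 0.656 | 0.916 / 0.973 / 0.948 | 0.992 / 0.998 / 0.996 |
| 8 | 0.931 / 0.822 / 0.565 | 0.058 / 0.168 / 0.430 | 0.942 / 0.944 / 0.962 | 0.989 / 0.990 / 0.995 |
| 10 | 0.840 / 0.886 / 0.650 | 0.028 / 0.107 / 0.349 | 0.924 / 0.967 / 0.930 | 0.989 / 0.994 / 0.987 |
| 20 | 0.947 / 0.921 / 0.876 | 0.001 / 0.012 / 0.122 | 0.975 / 0.956 / 0.957 | 0.975 / 0.978 / 0.989 |

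If 20 bleeds per regimen were also split evenly by age group, the n=10 row would apply.

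**What would be printed.** For an all-success cell the Wilson lower limit is n/(n + 1.96²) and the Clopper-Pearson lower limit is 0.025^(1/n).
- 4/4: normal approximation 100% to 100%; Wilson from 4/7.84 = 51%; Clopper-Pearson from 39.8%.
- 8/8: normal approximation 100% to 100%; Wilson from 8/11.84 = 67.6%; Clopper-Pearson from 63.1%.
- 4/5: normal approximation 44.9% to 115.1%; Wilson 37.6% to 96.4%; Clopper-Pearson 28.4% to 99.5%.

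**The case against.** The strongest reply is that the plan may not call for this interval at all. The interval sentence does not name severe bleeds, whereas the time-to-response paragraph that follows it does name them separately and combined. The rule written specifically for severe bleeds is the descriptive one in Section 9.5.1. If that excludes an interval, the problem never arises; if it allows one, the two sections do not conflict. This stands as far as it goes: a severe-only interval is inferred from the endpoint list, and the wording needs settling either way.

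The main SAP may also name another method, which cannot be checked. The age split applies only where applicable, and the addendum's stratified tables omit severe bleeds alone. No test or success rule uses the interval, and Section 9.1 already reports categorical variables with frequencies, so counts should appear beside the percentage.

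Some stronger readings are tempting but not supported:
- That only a handful of severe bleeds will occur. The protocol says only that they are a minority.
- That the interval is never close to 95%. At a 70% rate, coverage is 93% at n=8 and 95% at n=20.
- That a 4/4 result cannot exclude a rate below 50%. This depends on the method: Clopper-Pearson starts at 39.8%, Wilson at 51%.

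Finally, a correlation cannot be estimated from data in which every bleed succeeds, so a remedy that relies on estimating it would fail where it is most needed. That is why the fix below prespecifies the value.

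**Conclusion.** The point holds conditionally. Sections 9.5.1 and 9.6 need to be reconciled on whether severe bleeds receive an interval. If they do, the normal approximation is a poor choice in small cells. With 4 to 20 independent bleeds per regimen, coverage runs over 34-88% at a true rate of 90%, 56-92% at 80% and 68-95% at 70%. The zero-width result at 0% or 100% is certain from the formula; how often it occurs depends on the unknown count and rate. The defect is clearest at about 10 bleeds or fewer per cell, and fades at 20 with a rate near 70%. Clustering of bleeds within a child is not in these figures and would be expected to lower coverage further.

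A reader might infer that the trial's efficacy conclusion is at risk. It is not: this is a secondary summary, and the primary test and success rule do not use it.

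**What to change.** In Protocol Section 9.6, state that severe-bleed proportions, and any proportion with few successes or few failures, are shown as n/N with a Wilson or Clopper-Pearson 95% interval in place of the normal approximation. Note that repeated bleeds within a patient make the interval approximate.

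Where patients contribute several bleeds, divide n by a design effect with a prespecified correlation, such as the protocol's 0.1. For example, if 8 severe bleeds came from 4 children with 2 each, the design effect would be 1 + (2 - 1) × 0.1 = 1.1 and the effective n 8/1.1 = 7.27. The Wilson lower limit for 8/8 would then move from 67.6% to 7.27/(7.27 + 3.84) = 65.4%.

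Align Section 9.5.1 so that its descriptive-only wording either includes this interval or excludes any interval, and bring the main SAP into line. If the main SAP already specifies such a method, only the protocol text needs to change.

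The cost is a sentence or two and a different interval option in the program. All-success cells gain an interval with real width. Clopper-Pearson is conservative: its coverage is 97.5% or more in the cases tabulated, against 92-98% for Wilson.

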For the primary efficacy endpoint for the FDA, efficacy will be evaluated by comparing the percentage of mild/moderate bleeding episodes that are evaluated as being successfully treated to an objective performance criterion (OPC). LR769 will be regarded as effective when the success percentage is statistically significantly higher than the OPC. This OPC was determined by reviewing the literature on what the reported success is of the treatment with bypassing agents. However, due to the use of a different endpoint in this study vs. several different other ones in literature, an estimate of what the OPC should be is difficult. Several publications provide a wide range of bleeding treatment success at different timepoints depending on the type of efficacy assessment used. An OPC of 55% was chosen, taking into account the stringent criteria for success (including elements to more objectively judge treatment success) in this study.

In addition, as the primary efficacy endpoint for the EMA, the proportion of bleeding episodes (mild, moderate and severe combined) evaluated with a “good” or “excellent” response as assessed by the patient/parent (mild/moderate bleeding episodes) and the

physician (severe bleeding episodes) at 12 hours after first administration of the study drug will be calculated.

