## 9.7 Tertiary Efficacy Endpoints

The tertiary efficacy endpoints consist of the following:

- Proportion of bleeding episodes (mild/moderate and severe, separately and combined) with a “good” or “excellent” physician reported assessment of the efficacy at 12 hours (if available)
- Proportion of recurrences (defined as a bleeding in the same joint/anatomical location within 24 hours after an initial successful response)
- Proportion of bleeding episodes (mild/moderate and severe, separately and combined) requiring alternative treatment
- Proportion of bleeding episodes (mild/moderate and severe, separately and combined) with successful pain relief

For each treatment, the mean number of administrations and mean total amount of drug administered per bleeding episode (mild/moderate and severe, separately and combined) will

be summarized using descriptive statistics. Also a 95% CI for the true mean will be calculated based on normal approximation.

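### Section 9.6 gives the confidence interval for the good/excellent proportions no allowance for repeated bleeds in the same child; applied as written it is too narrow

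*Protocol*

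**What the plan says.** Protocol Section 9.6 treats two secondary proportions in consecutive paragraphs, each for the two regimens separately and together.

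- Success by the primary-endpoint criteria, over the timepoints: "a 95% CI for the true mean patient level proportion will be calculated based on normal approximation".
- Good or excellent patient-reported rating, at all timepoints: "a 95% CI for the true proportion will be calculated based on normal approximation".

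For the primary FDA endpoint, Section 9.5.1 also uses a normal-approximation interval, but "taking into account the correlation between bleeding episodes for a given patient in calculating the standard error". Section 9.2 plans the sample size with "a correlation among bleeding episodes for a given patient of 0.1" and notes that the standard error of the primary test statistic allows for it. Section 9.1 adds: "Where applicable, analyses will be done for all patients and by age group". It also leaves detail to another document: "Detailed methodology for the statistical analyses will be documented in a Statistical Analysis Plan (SAP"). The only SAP document supplied is an addendum to main SAP version 2.0. The addendum repeats the good/excellent proportions by age group and BMI tertile and states no standard error or interval method for them.

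On the number of administrations and the amount of drug per bleed, Section 9.7 says "Also a 95% CI for the true mean will be calculated based on normal approximation". The Synopsis (Efficacy Evaluation) specifies patient-level means and an interval across patients for the same quantities.

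**The concern.** The good/excellent proportion counts bleeding episodes, and each child is expected to contribute many. The protocol assumes that bleeds in one child are positively correlated and says so wherever it adjusts for this. The good/excellent sentence is the exception. A programmer who follows it as written would compute the square root of p(1−p)/n over bleeds, as if every bleed came from a different child.

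At stake is the stated precision of a listed secondary endpoint, per regimen, for both regimens together and by age group. The unadjusted intervals would also stand beside an adjusted primary interval and look tighter partly because of the method.

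**Working it through.** **Inputs.** From Section 9.2: 22 children, 8 mild/moderate bleeds per child per regimen (176 per regimen, 352 in all), correlation r = 0.1, true success 0.70, criterion 0.55, one-sided alpha 0.0125. The 0.70 and 0.1 were set for the FDA composite; using them for the good/excellent rating is an assumption.

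**The plan's own figure.** Design effect DE = 1 + (8 − 1) × 0.1 = 1.7, so the effective number of bleeds is 176/1.7 = 103.5.

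- se0 = √(0.55 × 0.45 × 1.7/176) = 0.0489
- se1 = √(0.70 × 0.30 × 1.7/176) = 0.0450
- Power = Φ((0.15 − 2.241 × 0.0489)/0.0450) = 81.5%

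This agrees with the stated 80% or more. Ignoring the correlation gives 97.2%, so the stated power is consistent with the correlation having been applied.

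**Interval per regimen.** The correct width is √DE times the unadjusted width. Coverage of the unadjusted interval is 2Φ(1.96/√DE) − 1. Only r = 0.1 is in the documents; the other values are assumed.

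| r | DE = 1 + 7r | factor √DE | unadjusted coverage |
|---|---|---|---|
| 0.02 | 1.14 | 1.07 | 93% |
| 0.05 | 1.35 | 1.16 | 91% |
| 0.10 | 1.70 | 1.30 | 87% |
| 0.20 | 2.40 | 1.55 | 79% |
| 0.30 | 3.10 | 1.76 | 73% |

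**Both regimens together.** Each bleed shares its child with 7 others in the same regimen and 8 in the other. With correlation c across regimens, DE = 1 + 7(0.1) + 8c.

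| c | DE | factor | unadjusted coverage |
|---|---|---|---|
| 0 | 1.7 | 1.30 | 87% |
| 0.05 | 2.1 | 1.45 | 82% |
| 0.10 | 2.5 | 1.58 | 78% |

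**In percentage points** (half-width = 1.96√(p(1−p)DE/n), r = 0.1). The good/excellent proportion is not given, so two values are shown; 0.90 is assumed.

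| | unadjusted | adjusted |
|---|---|---|
| per regimen, p = 0.70 | ±6.8 | ±8.8 |
| per regimen, p = 0.90 | ±4.4 | ±5.8 |
| combined, p = 0.70 | ±4.8 | ±6.2 to ±7.6 |
| combined, p = 0.90 | ±3.1 | ±4.1 to ±5.0 |

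**Simulation check** (beta-binomial, r = 0.1, p = 0.70, 40,000 runs). Coverage is given for the unadjusted interval, then for a cluster-adjusted standard error with normal quantiles, then with t quantiles.

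- 22 children, 8 bleeds each: 87.0%, 93.4%, 94.7%
- 22 children, 16 bleeds each: 78.4%, 93.3%, 94.7%
- 22 children, unequal bleeds (mean 8, assumed coefficient of variation 0.67): 82.5%, 92.0%, 93.4%
- 11 children (one age group), 8 bleeds each: 87.1%, 91.6%, 94.7%

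**Where the figures apply.** Eight rated bleeds per child is reasonable at timepoints where every mild/moderate bleed must be rated, such as 12 and 24 hours (Section 6.8; Appendix 1). At timepoints tied to further injections fewer bleeds per child are rated, and the factor is smaller. For severe bleeds alone, at an assumed 2 to 3 per child, DE is 1.1 to 1.2 and the factor 1.05 to 1.10.

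**The case against.** The strongest objection is that this is silence, not error. Normal approximation names the reference distribution, not the standard error, and Section 9.5.1 uses the same phrase with an adjusted standard error. Section 9.1 leaves detail to the SAP, and the main SAP is not in hand. This stands as a limit: a reader might infer that the trial computed, or will compute, unadjusted intervals, and the documents do not show that. It does not remove the point, because the sentence applied as written yields the wrong error bars and nothing supplied corrects it. The GEE and GLMM analyses in 9.5.1 are sensitivity analyses of the primary endpoint.

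It can also be said that the intervals are descriptive and no test depends on them. That is correct and limits the weight of the point.

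Three further inferences are tempting but unsupported:

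- **That the loss is the same at every timepoint.** It depends on how many bleeds per child are rated.
- **That the good/excellent proportion cannot fall below the FDA composite.** The Synopsis (Efficacy Evaluation) defines the composite as success by 12 hours, while other sections say at 12 hours. Under the Synopsis definition, a bleed rated good early and lower at 12 hours could count for the composite alone.
- **That the Kaplan-Meier intervals in the addendum's shell tables are also too narrow.** The addendum refers that method to the main SAP, and no defect is shown.

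Finally, an adjusted bleed-level interval and a patient-level interval are not interchangeable. When bleeds per child vary, the first concerns a bleed-weighted proportion and the second a mean of the children's proportions. That objection is sound, and the fix names one.

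**Conclusion.** The point holds for the protocol text. As written, the good/excellent interval in 9.6 makes no allowance for clustering and is too narrow. At the planning correlation of 0.1 with 8 bleeds per child, it should be about 1.30 times wider per regimen (unadjusted coverage about 87%) and 1.30 to 1.58 times wider for both regimens together (87% to 78%). Over assumed correlations of 0.02 to 0.30 the per-regimen factor runs from 1.07 to 1.76.

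This rests on three assumptions: the correlation carries over from the FDA composite, bleeds per child are equal, and nearly all bleeds are rated at the timepoint. In the simulation, unequal numbers lowered the unadjusted coverage further.

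The first secondary proportion needs no change. Confidence is limited by the absence of the main SAP. The mismatch between Section 9.7 and the Synopsis is separate and a matter of wording.

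**What to change.** In Section 9.6, state that the interval for the good/excellent proportions of bleeding episodes uses the same standard error as Section 9.5.1, adjusted for within-patient correlation. This keeps the bleed as the unit of the estimand. If main SAP version 2.0 already says this, a cross-reference is enough.

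The t quantiles are optional. They help most in the age-group tables of about 11 children, but 9.5.1 uses normal quantiles, so any difference should be stated.

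In Section 9.7, specify patient-level means and an interval across patients for the number of administrations and amount of drug, as the Synopsis does.

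The cost is a sentence or two, reuse of the primary-analysis code, and wider descriptive intervals. Coverage improves but is not exact: with 22 children, 8 bleeds each and p = 0.90, the simulation gives about 91% with normal and 92% with t quantiles.
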